Subjects that initially screen fail for the study may be permitted to re-screen following re-consent. All screening procedures with the possible exceptions noted below will be repeated. The subject must meet all inclusion and none of the exclusion criteria at the time of re-screening in order to qualify for the study. There is no minimum period of time a subject must wait to re-screen for the study. If the subject had a complete initial screening evaluation including tuberculosis (TB) screening, chest x-ray (CXR, if applicable), and 12-lead electrocardiogram (ECG), these tests will not be required to be repeated for re-screening provided the conditions noted in Section 5.3.1.1 are met and no more than 3 months (90 days) have passed. As appropriate, study sites are encouraged to contact the AbbVie Medical Monitor to confirm if subjects should or should not be

re-screened. If the subject had a negative human immunodeficiency virus (HIV) result at screening but 30 days have elapsed prior to the re-screen, then the HIV screening test must be repeated and the result handled in a like manner as the original screening test (see Section 5.3.1.1).

Period A: A 12-week double-blind, placebo-controlled treatment period during which subjects are randomised in a 1:1 ratio to receive adalimumab or matching placebo, 160 mg initially at Day 1 (or given as two 40 mg injections per day for 2 consecutive days), followed by 80 mg 2 weeks later at Day 15 (given as two 40 mg injections in 1 day). Two weeks later (Day 29) continue with a dose of 40 mg ew until Week 12. The randomisation will be stratified by baseline Hurley Stage (II versus III) and anatomical location of the surgical site (i.e., axilla versus inguinal region). A subject's Hurley Stage is determined by the worst Hurley Stage (i.e., II versus III) across all affected anatomic regions. The projected size of the surgical excision established by the designated surgeon during the Screening Period (calculated from a tracing of the outer perimeter onto an acetate sheet or equivalent) will be recorded by the study physician in the CRF. On each clinical study visit day, all study procedures scheduled for that visit will be completed prior to study drug administration.

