5.5 Treatments

5.5.1 Treatments Administered

All treatments administered will be assigned via Interactive Response Technology (IRT) in order to maintain blinding. During Period A (Week 0 through Week 12), all subjects will receive 4 injections initially at Day 1 (or alternatively, given as two 0.8 mL injections per day on 2 consecutive days), 2 injections at Day 15 (Week 2), and one injection weekly

from Week 4 through Week 12. During Period B, all subjects will receive one injection weekly from Week 13 through Week 14. During Period C, all subjects will receive one injection weekly from Week 15 through Week 23. No study drug will be administered at the Week 24 or Premature Discontinuation Visit.

Study drug will be provided as a sterile, preservative-free solution for subcutaneous (SC) administration in 1 mL pre-filled syringes containing adalimumab 40 mg/0.8 mL or placebo (0.8 mL). The subject should be instructed to store the pre-filled syringe in the outer carton (in order to protect from light) in the refrigerator at 2° to 8°C/36° to 46°F, and that syringes should not be stored in a freezer.

Study drug will be administered SC using sterile technique by the subject or designee (e.g., family member, friend, health care professional) at the study site, or at home via self-injection following proper training ([Appendix P](#)) or by a qualified designee. At each Study visit qualified research personnel will observe the subject or designee during the injection to ensure proper technique. The subject should place the used syringe in the sharps disposal container, which will be provided to the subject at each study visit (unless prohibited by local regulations) or less frequently depending upon the size of the container.

Period A

Subjects randomised to Arm 1 will receive:

- 160 mg/3.2 mL adalimumab at the Baseline Study visit (Day 1) administered as four 40 mg injections SC (or two 0.8 mL injections on two consecutive days, i.e., Day 1 and Day 2)
- 80 mg/1.6 mL adalimumab at the Week 2 (Day 15) Study visit administered as two 40 mg injections SC
- 40 mg/0.8 mL adalimumab every week (ew) from Week 4 (Day 29) through Week 12 administered (either at the Study visit or at home as appropriate) as one 40 mg injection SC

Subjects randomised to Arm 2 will receive:

- 3.2 mL placebo at the Baseline Study visit (Day 1) administered as four 40 mg injections SC (or two 0.8 mL injections on two consecutive days, i.e., Day 1 and Day 2)

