5.5.4 Selection and Timing of Dose for Each Subject

Subjects should take study medication as outline in Section 5.5.1.

At the Baseline visit, after all assessments have been completed, subjects in Arm 1 will receive four injections of active study drug (40 mg/0.8 mL each) and subjects in Arm 2 will receive four placebo injections (0.8 mL each) as detailed in Section 5.5.1.

Appropriate study site personnel will train and then supervise the subject or designee administering at least one injection of the study drug to ensure proper understanding of injection technique (Appendix P). The subject or designee will subsequently dose and be witnessed by study site personnel during their study visits to ensure continued proper technique. When study drug is administered at the Day 1 (Week 0) and Week 2 study visits (see Appendix C), the subject should remain at the study site for approximately 15 to 30 minutes after injection for observation.

For home administration of injection, subjects or qualified designee will be instructed to inject study medication on the same day of the week as their Baseline visit day as detailed in Section 5.5.1. Every kit contains 2 syringes each.

If a subject should forget to administer the injection of study medication on their regularly scheduled dosing date, the subject should take the forgotten injection as soon as she/he remembers the dose was missed up to the day before the next scheduled dose. The subject should not administer two doses on the same day.

Doses not administered (e.g., not taken before the next dose is scheduled), should be recorded as not taken in the source. The extra dose should be returned in its entirety to the study site at the subject's next study visit. Meanwhile, the subject should resume their regular dosing schedule based on the first dosing date at Baseline (Day 1).

In the event the incorrect dose is taken, the entire volume of study drug is not injected, or a dose is missed, the subject should be instructed to contact the study site to determine how to proceed with dosing. The subject must record all dosing information on the Subject-Dosing Diary Sheet.

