Appendix O. Clinical Study Site Personnel – Study Drug Dispensing Table

Visit	Dose	Dispense Study Drug for Weeks**	Number of Syringes Used Day of Visit	Number of Kits and Syringes per Kit Dispensed for Between Visits
Baseline	160 mg (1st loading dose)	Week 1 (D1 or split over D1+D2)	4 (or 2 if split on two days)	2 kits (4 syringes)
Week 2	80 mg (2nd loading dose)	Week 2 (Day 15) 40 mg/week	2	1 kit (2 syringes)
Week 4	40 mg/week	Weeks 4, 5, 6 and 7	1	2 kits (4 syringes)
Week 8	40 mg/week	Weeks 8, 9, 10, and 11	1	2 kits (4 syringes)
Week 12	40 mg/week	Weeks 12, 13, 14 and 15	1	2 kits (4 syringes)
Week 15	40 mg/week	Weeks 16 and 17	1	1 kit (2 syringes)
Week 17	40 mg/week	Weeks 18, 19, 20 and 21	1	2 kits (4 syringes)
Week 20	40 mg/week	Weeks 22, and 23	1	2 kits (4 syringes) resulting in 1 kit/2 PFS* left over at study's end which should be destroyed if not being used as replacement.

* PFS = Pre-filled syringes.

** Study Investigators will ensure that enough study drug is dispensed at each visit to cover the subject until their next visit.

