Appendix P. Subject Injection Instructions – Example Pre-Filled Syringe

1. You will not administer injections to yourself at home on clinic visit days. You or your helper will be taught on a clinic visit day how to give injections subcutaneously (under the skin, not in the muscle) and you will be asked to show the study staff you or your helpers ability to self-inject in the clinic.
2. You will administering injections at home on Day 2 of Week 0 (if directed by your study doctor), on the first day of Weeks 5, 6, 7, 9, 10, 11, (ask your study doctor about Weeks 13 and 14), and on the first day of Weeks 16, 18, 19, 21, 22 and 23 (last dose).
3. Check your dosing chart to make sure you are giving yourself the injection on the same day of the week as your last injection and check the location of the last injection on your home chart so you choose a different location for the current injection
4. Remove your carton from the refrigerator and remove **one** pre-filled syringe (there will be two syringes in the carton). Put the other syringe (syringe 2) back in the carton and place the carton back in the refrigerator.
5. If your pre-filled syringe accidentally becomes frozen, do not use the syringe and contact your study doctor.
6. Prepare a clean area where you will not be distracted.
7. You may self-administer your injection or have a helper, someone who has been approved by the study staff, do so.
8. Check the syringe to make sure the fluid in the syringe is clear and colorless. If you notice anything unusual about the pre-filled syringe, such as the liquid is cloudy, discolored or has flakes in it or the syringe itself doesn't look right to you, contact your study doctor before administering your injection. If there is a question or something unusual suspected by your study doctor, you may be required to return the carton with the full liquid amount in the syringe to your study doctor if requested to do so.

9. Wash your hands with soap and warm water or have your helper do the same. Clean medical gloves are not necessary but may be preferred by your helper.
10. If you or your helper is ready to administer your injection, have your alcohol swab, sharps container (a safe place to put your used syringes) and gauze or cotton ball ready.
 - a. As you or your helper was taught in the clinic, you will first swab the area with alcohol, being careful to go from the inside out in a circular motion, trying not to put alcohol on the same area of your skin twice.

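### Appendix P steps 3 and 4 make no exception for Day 2 of a split loading dose; read literally, a subject injecting at home takes 40 of 80 mg unless the second syringe is made up by Day 14

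*Protocol*

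**What the plan says.** Three places in the protocol define the split first loading dose, and they agree. Section 5.1.1 gives "160 mg initially at Day 1 (or given as two 40 mg injections per day for 2 consecutive days". Section 5.5.1 has the dose "administered as four 40 mg injections SC (or two 0.8 mL injections on two consecutive days, i.e., Day 1 and Day 2". The Baseline row of Appendix O lists two kits (four syringes) and, for the number used on the visit day, "4 (or 2 if split on two days", which leaves two syringes for Day 2.

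Appendix P is the subject's own instruction sheet, headed as an example. Its step 2 covers the split: "You will administering injections at home on Day 2 of Week 0 (if directed by your study doctor". Step 3 then says "Check your dosing chart to make sure you are giving yourself the injection on the same day of the week as your last injection". Step 4 says to remove one "pre-filled syringe (there will be two syringes in the carton). Put the other syringe (syringe 2) back in the carton" and to return the carton to the refrigerator. The only later use given for syringe 2 is in step 10f, as a replacement when blood appears in the first syringe.

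**The concern.** Step 2 brings Day 2 within the scope of the hand-out, but steps 3 and 4 describe a weekly one-syringe dose. Day 2 differs on both counts: it falls one day after the last injection and it needs both syringes. No step says so.

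A subject who follows step 4 as written takes half the Day 2 dose. Only the adalimumab arm loses drug, since a placebo subject merely omits one placebo syringe, so any effect on efficacy would tend to shrink the treatment difference. An incorrect dose is also a reportable deviation under Section 7.0, so following the sponsor's hand-out could itself produce one.

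**Working it through.** **Inputs**
- Syringe strength: 40 mg in 0.8 mL (Section 5.5.1).
- Baseline supply: 2 kits of 2 syringes (Appendix O).
- Second loading dose: 80 mg at Week 2, Day 15 (Section 5.5.1).
- Make-up rule for a missed injection (Section 5.5.4): "take the forgotten injection as soon as she/he remembers the dose was missed up to the day before the next scheduled dose".
- Week 2 visit window: ±3 days; telephone calls at Weeks 6 and 10 (Section 5.1.1).

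**Intended dose (reproduces the plan's figure)**
- Unsplit: 4 × 40 = 160 mg (4 × 0.8 = 3.2 mL).
- Split: 2 × 40 = 80 mg (1.6 mL) on each of Days 1 and 2; 80 + 80 = 160 mg.
- Syringes: 2 × 2 = 4 dispensed, less 2 used on Day 1, leaves 2 for Day 2. Supply and dose agree.

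**Dose if step 4 is followed literally and the second syringe is not made up**

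| | Intended | Taken | Shortfall |
|---|---|---|---|
| Day 2 | 80 mg | 1 × 40 = 40 mg | 40/80 = 50% |
| First loading dose | 160 mg | 80 + 40 = 120 mg | 40/160 = 25% |
| Through Week 2 | 160 + 80 = 240 mg | 120 + 80 = 200 mg | 40/240 = 16.7% |

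One syringe is left over (4 − 2 − 1 = 1). In the placebo arm the same reading means 3 of 4 syringes.

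**Dose if the second syringe is made up**
- Last permitted day: 15 − 1 = Day 14.
- Delay: from 3 − 2 = 1 day to 14 − 2 = 12 days; 0 mg lost.
- Day 14 uses the nominal Day 15 dose. If the Week 2 dose moves within its window (Days 12 to 18), the last make-up day moves to between 12 − 1 = Day 11 and 18 − 1 = Day 17.

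**Weekday check in step 3**
- Day 2 − Day 1 = 1 day, not a multiple of 7, so the check cannot be met. Applied strictly it would bar any Day 2 injection, which contradicts step 2.

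**Chance of correction before the window closes**
- The next scheduled contact after Day 2 is the Week 2 visit, when the next loading dose is itself due. The calls at Weeks 6 and 10 come later.
- A make-up therefore depends on the subject recognising the omission or contacting the site. Step 13 asks for unused syringes to be brought back, so a left-over syringe need not look wrong to the subject.

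**The case against.** The strongest reply is that the hand-out does not act alone. Home dosing on Day 2 happens only at the study doctor's direction. Under Section 5.5.4, site staff "train and then supervise the subject or designee administering at least one injection of the study drug", and the subject will have had two syringes at the visit the day before. Step 14 tells the subject to call if a full dose cannot be given, Section 5.5.4 allows a late injection, and Section 5.5.7 has returned supplies checked at visits. Appendix P is an example, and the dosing chart that step 3 refers to (Appendix Q) is not in the text available here; it may show two injections for Day 2. Steps 4 to 12 can also be read as handling for one injection, to be gone through twice. Finally, the 40 mg figure depends on applying step 4 strictly while setting step 3 aside.

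Much of this stands, and it is why the point is minor. The ordinary outcome may well be that both syringes are taken on Day 2 as directed. But step 14 and the make-up rule help only a subject who realises that an injection was missed, and someone who has done what step 4 says gets no such cue from the hand-out. The repeat-for-each-injection reading is possible but unstated; where the hand-out does want a repeat with syringe 2 (step 10f), it says so and ties it to blood in the syringe. Whichever of steps 3 and 4 is taken strictly, neither agrees with a two-syringe Day 2 dose.

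**Conclusion.** The concern holds as a minor wording error in a subject hand-out. For an affected adalimumab subject the range is:
- both syringes taken on Day 2 despite the wording: nothing lost, no delay;
- second syringe made up between Day 3 and Day 14: nothing lost, 40 mg given 1 to 12 days late;
- second syringe never taken: 40 mg lost, with the shortfalls tabulated above.

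This rests on a literal reading of Appendix P, on the nominal Day 15 dose, and on Appendix Q not already giving the correct instruction, which could not be checked. The documents do not say how many subjects would inject at home on Day 2, so no effect on the Week 12 HiSCR rate is estimated; it is probably small. The sample size, significance level and planned analyses are unaffected.

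**What to change.** Add to Appendix P step 4: *On Day 2 of Week 0, if your study doctor split your first dose, use both syringes: repeat the injection steps with the second syringe at a different site.* Add to step 3 that the same-weekday check does not apply on Day 2. Confirm that Appendix Q shows two injections for that day.

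Sections 5.5.1 and 5.5.4 and Appendix O need no change. The cost is two sentences in a hand-out, with no extra visits, staff, subjects, drug supply or analyses.

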Appendix R. Study Site Drug Accountability (by Subject) Log – Example

Subject Number	Kit Number	Date Dose Administered	Total Dose Administered (mg)	Total Volume Administered (mL)	Start Time of Dose	End time of Dose
					:	:
					:	:
					:	:
		Administered By (Sign and Date)			Verified By (Sign and Date)	

I attest that the subject identified by number above, or designated helper (documented in source document as having been trained), has demonstrated safe administration of study drug on Date: _____ Time: _____ and the subject is approved to self-administer or have study drug administered by their designated (trained) helper.

Name of Study Investigator or Designee

Signature of Study Investigator Designee

Appendix S. Protocol Amendment: List of Changes

The summary of changes is listed in Section 1.1.

Specific Protocol Changes

Section 1.0 Title Page

"Sponsor/Emergency Contact:" previously read:

Sponsor/Emergency
Contact:

[REDACTED]
Global Medical Affairs
[name]
[name]
France

Phone: [REDACTED]
Cell: [REDACTED]

Has been changed to read:

Sponsor/Emergency
Contact:

[REDACTED]
Global Medical Affairs
[REDACTED]
[name]
[name]

Phone: [REDACTED]
Cell: [REDACTED]

Section 1.2 Synopsis

Subsection Study Sites:

Previously read:

Investigator information is on file at AbbVie.

Has been changed to read:

The planned number of sites for this study is 56.

Section 6.1.5 Adverse Event Reporting
"Study Designated Physician:" previously read:

[REDACTED]
[name]
[name] France

Telephone Contact Information:

Office: [REDACTED]
Mobile: [REDACTED]
Email: [REDACTED]

Has been changed to read:

[REDACTED]
[name]
[name]

Telephone Contact Information:

[figure not shown]
Office: [REDACTED]
Mobile: [REDACTED]
Email: [REDACTED]

Section 7.0 Protocol Deviations
"Alternate Contact:" previously read:

[figure not shown]
[REDACTED]
[name]
[name]

Office: [REDACTED]
Email: [REDACTED]

Has been changed to read:

[name]
[name]

Office: 
Mobile: 
Email: 

[figure not shown]
[figure not shown]
[figure not shown]
[figure not shown]
[figure not shown]
[figure not shown]
[figure not shown]
Section 8.1.4.1 Primary Analysis of Efficacy
First paragraph
Add: new last sentence

The 95% confidence intervals of treatment difference will also be provided.

Section 8.1.4.1 Primary Analysis of Efficacy
Add: new last paragraph

In addition, a sensitivity analysis controlling for change from baseline in body weight using logistic regression models, for the primary efficacy endpoint. Analysis details will be specified in the SAP prior to study unblinding and prior to database lock.

### 3.0 Introduction

This Statistical Analysis Plan (SAP) describes the statistical analysis for adalimumab study Protocol Study M15-574. It provides high level summaries of the planned statistical analyses for key efficacy and safety endpoints, interim analysis and multiplicity control strategies. Further details and analysis conventions to guide the statistical programming work will be in a supplement document.

Analyses will be performed using SAS® version 9.4 (SAS. Institute, Inc., Cary, NC 27513) or higher using the UNIX operating system.

[figure not shown]
SAP will not be updated in case of future administrative or minor amendments to the protocol unless the changes have an impact on the analysis of the study data.

### 4.0 Study Background

### 4.1 Objective

The primary objective of this study is to assess the safety and efficacy of adalimumab prior to surgery in subjects with moderate to severe HS who are surgical candidates, using Hidradenitis Suppurativa Clinical Response (HiSCR, defined as at least a 50% reduction in the HS abscess plus inflammatory nodule [AN] count with no increase in abscess count and no increase in draining fistula count relative to Baseline) as the assessment measurement.

Secondary objectives of this study include: Assess the impact of adalimumab specifically on the planned HS surgical site before surgery, evaluate the safety and efficacy of adalimumab continued during the perioperative period and after surgery, and evaluate Patient Reported Outcomes (PRO) related to health status, HS-related symptoms (e.g., drainage, swollen skin), physical functioning, treatment satisfaction, and work/activity impairment. The pharmacokinetics (PK) and immunogenicity of adalimumab following subcutaneous (SC) injection in this HS surgical population will

also be assessed. The objective is to determine if the inflammatory status of the HS surgical subject alters the PK profile both prior to and after surgery.

### 4.2 Study Design

[figure not shown]
### 4.2.1 Study Design and Design Diagram

This interventional, randomised, double-blind, placebo-controlled study is designed to enroll 200 subjects to meet scientific and regulatory objectives without enrolling an undue number of subjects in alignment with ethical considerations. Therefore, if the target number of subjects has been enrolled, there is a possibility that additional subjects in screening will not be enrolled. Eligible subjects will have active HS disease with an axilla or unilateral inguinal region that requires excisional surgery plus two other anatomical regions with active HS lesions (at least one region at Hurley Stage II or III).

The study duration will include an up to 30-day Screening Period, an initial 12-week double-blind treatment pre-surgery period (Period A), a 2-week peri-surgery period with continuation of weekly double-blind study drug administration (Period B), and a subsequent 10-week double-blind treatment post-surgery period (Period C).

**Screening Period:** The duration of the screening period will be a minimum of 7 days and a maximum of 30 days during which time all of the inclusion and exclusion criteria will be evaluated, and at referring sites, an eligibility visit with the designated surgeon will take place. Subjects may enroll into the study after all screening procedures are complete and results are known and verified for eligibility at the Baseline visit (Day 1) to receive 160 mg of adalimumab or matching placebo.

**Period A:** A 12-week double-blind, placebo-controlled treatment period during which subjects are randomised in a 1:1 ratio to receive adalimumab or matching placebo, 160 mg initially at Day 1 (or given as two 40 mg injections per day for 2 consecutive days), followed by 80 mg 2 weeks later at Day 15 (given as two 40 mg injections on a single day). Two weeks later (Day 29) continue with a dose of 40 mg ew until Week 12. The randomisation will be stratified by baseline Hurley Stage (II versus III) and anatomical

location of the surgical site (i.e., axilla versus inguinal region). A subject's Hurley Stage is determined by the worst Hurley Stage (i.e., II versus III) across all affected anatomic regions. The projected size of the surgical excision established by the designated surgeon during the Screening Period (calculated from a tracing of the outer perimeter onto an acetate sheet or equivalent) will be recorded by the study physician in the CRF. On each clinical study visit day, all study procedures scheduled for that visit will be completed prior to study drug administration.

[figure not shown]
**Period B:** A 2-week double-blind, placebo-controlled treatment period consisting of Weeks 13 and 14 (the peri-operative period) in which subjects will continue the treatment on the first day of Weeks 13 and 14. The designated surgeon will measure the surface area of the actual surgery and record in source document. Surgery will occur during Week 13. The surgery and post-operative management (e.g., hospitalisation, surgical wound care) will be as per local practice.

**Period C:** A 10-week double-blind, placebo-controlled post-operative treatment period will occur from Week 15 through Week 24, during which the subject will continue the treatment assigned at Day 1 from Week 15 through Week 23. No study drug will be administered at Week 24, the final study visit. Subjects may begin commercial product (as prescribed by the subject's physician) after all Week 24 procedures have been completed.

Subjects will be contacted approximately 70 days following study drug discontinuation for an assessment of any new or ongoing AEs/SAEs, except for those subjects who continue on adalimumab not supplied in the context of the clinical trial after the end of study participation. These subjects are not required to complete the 70-day follow-up telephone call and any new AEs should be reported through the mechanism used for all post-marketing adverse experience.

The schematic of the study is shown in Figure 1. Further details regarding study procedures are located in study protocol Appendix C.

[figure not shown]
Figure 1. Study Schematic

See Section 5.2 of the protocol for information regarding eligibility criteria. Study sites and subjects will remain blinded for the duration of the study.

